12.5. Audit and Inspection

The Investigator will agree to receive periodic quality assurance audits conducted by the Sponsor's clinical quality assurance personnel or its designee. In addition, the Investigator will agree to inspections by regulatory agencies to the extent permitted by law. Auditors and inspectors will have direct access to all relevant study documentation.

12.6. Source Documents

The Investigator must allow regulatory agencies, individuals delegated by the IRB/IEC or the Sponsor or its designee to have access to all the original documentation of the study, including the ICFs signed by the patients enrolled into the study and the relevant patient medical files. The individuals who are given access to the documentation must take every reasonable precaution to keep the identity of the patients and the proprietary information of the Sponsor as confidential information in accordance with relevant applicable legislation.

12.7. Electronic Data Capture

Electronic Case Report Forms (eCRFs) will be supplied by the Sponsor or its designee and should be handled in accordance with the provided instructions. All eCRFs should be filled out completely by authorized study personnel.

The Investigator should ensure the accuracy, completeness and timeliness of the data recorded on the eCRF. Data recorded on the eCRF will be consistent with source documents. Any discrepancies must be explained or resolved.

Completed eCRFs will be reviewed by the Sponsor's monitoring staff or its designee. An eCRF will be completed for each patient enrolled in the study.

12.8. Premature Termination of the Study

If the study is prematurely terminated or suspended, the Sponsor will promptly inform the investigators and the regulatory authority(ies) of the reason(s) for termination or suspension. The IRB/IEC also will be promptly informed by the Sponsor or Investigator and provided with the reason(s) for the termination or suspension, as specified by the applicable regulatory requirement(s).

12.9.Study Report

The results of the study will be presented in an integrated clinical study report according to GCP and ICH-E3 guidance. The Sponsor will ensure that the clinical study reports are prepared and provided to the regulatory agency(ies) as required by the applicable regulatory requirement(s). The Principal Investigator will submit to the Sponsor a copy of the report issued to the IRB/IEC.

Confidentiality Statement

12.10. Finance, Insurance and Publication

Insurance coverage will be handled to local requirements.

Finance, insurance and publication rights are addressed in the Investigator/Institution and/or CRO agreements as applicable.

12.11. Archiving and Data Retention

The Investigator shall retain adequate records for the study including copies of each patient's eCRFs, medical records, laboratory reports, ICF(s), IMP accountability records, safety reports, information regarding patients who were withdrawn and any other pertinent data. The Investigator must retain all records for at least 20 years after completion or discontinuation of the trial or at least 2 years after the last approval of a marketing application in an ICH region and until there are no pending or contemplated marketing applications in an ICH region or until at least 2 years have elapsed since the formal discontinuation of clinical development of the investigational product. These documents should be retained for a longer period however if required by the applicable regulatory requirements. The sponsor will notify the investigator when the records no longer need to be kept.

If the responsible Investigator retires, relocates or for other reasons withdraws from the responsibility of keeping records, custody must be transferred to a person who will accept the responsibility. The Sponsor will be notified in writing of the name and address of the new custodian as soon as possible.

12.12.Confidentiality

The Investigator must assure that patients' anonymity will be strictly maintained and that their identities are protected from unauthorized parties. The patient's identification code and the patient's initials should be recorded on any form submitted to the Sponsor, Sponsor's designee, or IRB/IEC, unless it is forbidden to identify the patient by initials. Where it is forbidden to indicate the patient's initials, only the patient's identification code and the patient's year of birth should be recorded.

The Investigator must keep a screening log showing codes, names and addresses for all patients screened and for all patients enrolled into the trial.

AST	Aspartate Aminotransferase
AUC	Area Under the Curve
BMI	Body Mass Index
BUN	Blood Urea Nitrogen
CFU	Colony Forming Units
CGM	Continuous Glucose Monitor
CMV	Cytomegalovirus
CRO	Contract Research Organization
CRF	Case Report Form
CRP	C-Reactive Protein
CSP	Clinical Study Protocol
CTCAE	Common Terminology Criteria for Adverse Events
DSMB	Data Safety Monitoring Board
DSMB-SAP	Data Safety Monitoring Board Statistical Analysis Plan
EBV	Epstein-Barr Virus
ECG	Electrocardiogram
eCRF	Electronic Case Report Form
eGFR	Estimated Glomerular Filtration Rate
GAD65	Glutamic Acid Decarboxylase 65
HbA1c	Hemoglobin A1c
HBV	Hepatitis B Virus
HCV	Hepatitis C Virus
HDL	High Density Lipoproteins
hIL-10	Human Interleukin 10
HIV	Human Immunodeficiency Viruses
hPINS	Human Proinsulin
IA-2	Insulinoma-Associated Protein 2
IAP	Interim Analysis Plan

ICH	The International Council for Harmonisation of Technical Requirements for Pharmaceuticals for Human Use
IDAA1c	Insulin dose adjusted HbA _{1c}
IMP	Investigational Medicinal Product
INR	International Normalized Ratio
IV	Intravenous
ITT	Intention to Treat
LDH	Lactate dehydrogenase
LDL	Low Density Lipoproteins
MedDRA	Medical Dictionary for Regulatory Activities
MCH	Mean Corpuscular Hemoglobin
MCHC	Mean Corpuscular Hemoglobin Concentration
MCV	Mean Corpuscular Volume
MMTT	Mixed Meal Tolerance Test
PCR	Polymerase Chain Reaction
PD	Pharmacodynamic
PD-ITT	Pharmacodynamic Intention To Treat
PD-PP	Pharmacodynamic Per Protocol
PK	Pharmacokinetic
PP	Per Protocol
PT	Preferred Term
RBC	Red Blood Cell
RDW	RBC Distribution Width
SAE	Serious Adverse Event
SAP	Statistical Analysis Plan
SD	Standard Deviation
SEM	Standard Error of the Mean
SOC	System Organ Class
TD1	Type 1 Diabetes Mellitus
TEAE	Treatment-Emergent Adverse Event
TSH	Thyroid Stimulating Hormone
VLDL	Very Low Density Lipoproteins
WBC	White Blood Cell
WHO	World Health Organization
ZnT8	Zinc Transporter 8

1 INTRODUCTION

This Statistical Analysis Plan (SAP) is based on Clinical Study Protocol (CSP) Version 9, dated June 10, 2020. This includes all analysis to be performed by XXX. The Pharmacokinetic (PK) analysis, the analysis regarding the Mixed Meal Tolerance Test (MMTT), the analysis of immune markers and the mechanistic assessments that will be performed by other Contract Research Organizations (CROs) are not included.

2 STUDY OBJECTIVES

2.1 Primary Objective

The primary objective of this study is to assess the safety and tolerability of different doses of encapsulated AG019, containing genetically modified *Lactococcus lactis* (*L. lactis*) producing human proinsulin (hPINS) and human interleukin-10 (hIL-10) (sAGX0407), alone as well as in association with teplizumab.

2.2 Secondary Objectives

The secondary objectives of this study are:

- to obtain pharmacodynamics (PD) data of AG019 alone as well as AG019 in association with teplizumab,
- to determine the potential presence of sAGX0407 or its secreted proteins in systemic circulation (safety – systemic exposure) and the presence of *L. lactis* bacteria in fecal excretion (local exposure): pharmacokinetic profile

3 EFFICACY AND SAFETY ENDPOINTS

3.1 Primary Endpoint

The primary endpoint will be assessed by analysis of the incidence of treatment-emergent adverse events (TEAEs) collected up to the 6-month follow-up visit. A TEAE is defined as any adverse event (AE) not present prior to the initiation of the treatment(s) or any AE already present that worsens in either intensity or frequency following exposure to the treatment(s).

3.2 Secondary Endpoints

The PD activity of the study drug(s) is assessed by measurement of biomarkers in blood and serum samples. Relevant parameters are assessed, including immune markers for effect, relevant T1D parameters and relevant cytokines. These will be presented by another CRO and thus will not be a part of the statistical analysis described in this SAP. This SAP will only discuss hemoglobin A1c (HbA1c), insulin use and insulin dose adjusted HbA1c as PD variables as these will be analysed by XXX.

Samples intended for mechanistic assessments are collected from all repeat dose patients in AG019 Cohorts 2 and 4, and from all patients in the combination cohorts. All collected samples intended for mechanistic assessments are planned to be analyzed by a central lab and will not be a part of the statistical analysis in this SAP.

Following parameters are assessed for analysis of systemic and local exposure to *L. lactis* (PK profile):

- Presence of live *L. lactis* clinical strain bacteria in whole blood
- Measurable serum levels of human interleukin 10 (hIL-10) and human proinsulin (hPINS)
- Presence of *L. lactis* clinical strain bacteria in fecal excretion

The PK profile will be presented by Precigen Actobio so PK will not be a part of this SAP.

Safety information collected at all other time points (all Adverse Events (AEs), laboratory variables, vital signs, physical examination, electrocardiogram (ECG), viral status, hypoglycemic events, hyperglycemic events, study drug accountability and concomitant medication) will be assessed as secondary endpoints and analysed by XXX.

4 OVERALL STUDY DESIGN

4.1 Overview of Study Design

This Phase 1b/2a, multi-center study is conducted in patients with clinical recent-onset Type 1 Diabetes Mellitus (T1D).

AG019 is the genetically modified *L. lactis*, strain sAGX0407, containing the gene sequences coding for hPINS and hIL-10, and comprising an environmental containment system, formulated for oral administration as gastro-resistant hard capsules.

In addition to the scheduled 19 clinic visits, all patients were asked to keep a diary for collection of information relating to the study drug intake, concomitant medication intake, occurrence of AEs including hypoglycemic and hyperglycemic events, and insulin use. A detailed schedule on the measurements for each visit can be found in the Appendix A to the CSP. Information on when the measurements were planned to be collected can also be found under each subsection in this SAP.

Eight (8) single dose patients and a maximum of 48 repeat dose patients were allowed to be enrolled in clinical sites in the US and Belgium. AG019 was administered twice daily for 8 weeks at either a low dose (2 capsules/d) or at a high dose (6 capsules/d). This study consists of 2 phases and 6 cohorts. All repeat dose patients in all cohorts described below will be followed up for a total of 12 months (8 weeks of treatment plus 10 months of post-treatment follow-up).

4.1.1 Phase 1b

This open-label part of the study will investigate the safety and tolerability of different doses of AG019, in 2 age groups (18-42 years of age and 12-17 years of age, respectively), administered as single or repeat doses. Patients were enrolled in 4 sequential cohorts (AG019 cohorts):

- **AG019 Cohort 1:** 2 capsules per day, patients 18-42 years
- **AG019 Cohort 2:** 6 capsules per day, patients 18-42 years
- **AG019 Cohort 3:** 2 capsules per day, patients 12-17 years
- **AG019 Cohort 4:** 6 capsules per day, patients 12-17 years

Single dose patients

In every AG019 cohort, 2 single dose patients were enrolled in a first stage. Each of these patients were treated for 1 day with AG019 (2 or 6 capsules of XXX Colony Forming Units [CFU], depending on the cohort), and were followed up for a total of 4 days (treatment day [Day 1] plus 3 additional days), after which they had completed their study participation (Day 4).

Repeat dose patients

A minimum of 4 repeat dose patients were enrolled per AG019 cohort. In addition, both single dose patients in each AG019 cohort were offered the option of being re-enrolled as repeat dose patients in the same AG19 cohort. Therefore, if both single dose patients agree to be re-enrolled as repeat dose patients, the maximum number of repeat dose patients per cohort were 6. All repeat dose patients were planned to be treated for 8 weeks with AG019 and followed up for a total of 12 months (8 weeks of treatment plus 10 months of post-treatment follow-up).

4.1.2 Phase 2a

The Phase 2a double-blind portion of the study will investigate the safety and tolerability of AG019, in association with intravenous (IV) teplizumab in 2 cohorts (“combination cohorts”) of 12 patients. Each patient is planned to be administered 6 capsules daily of AG019 (or placebo) for 8 weeks, in association with daily IV infusions of teplizumab (or placebo) for the first 12 days of the 8-week treatment period.

- **Combination Cohort 1:** 12 patients (18-40 years) received AG019 (6 capsules per day, 8 weeks) plus teplizumab (daily infusions, 12 days), or matching placebo capsules and placebo infusions
- **Combination Cohort 2:** 12 patients (12-17 years) received AG019 (6 capsules per day, 8 weeks) plus teplizumab (daily infusions, 12 days), or matching placebo capsules and placebo infusions

Within each of these combination cohorts, the first 2 enrolled patients were treated with active treatment (AG019 plus teplizumab) in an open label fashion. Patients 3-12 were randomized (4:1) to receive double active treatment or double placebo in a double-blind fashion.

4.2 Determination of Sample Size

In total, 8 single dose patients and up to 48 repeat dose patients were planned to be enrolled.

This is a preliminary study designed to provide information to be used in the design of subsequent studies. This study is descriptive in nature and is not designed to provide analytical results regarding efficacy. As such, the sample size is not based on statistical considerations, rather it is believed that at least 4 patients per dose level in the AG019 cohorts and 12 patients

in the combination cohorts will provide sufficient data to evaluate preliminary safety and activity of the Investigational Medicinal Products (IMP) as administered in the protocol.

Patients who discontinued after entry into the treatment phase were allowed to be replaced if approved by the Sponsor.

5 DATA SETS TO BE ANALYZED

The following analysis sets will be used for the statistical analysis and presentation of data:

- **The Safety (SAF) Analysis Set.** The safety population will include all patients who received at least one dose of AG019. Only patients with clear documentation that no study medication was received may be excluded from analysis. Patients will be analyzed according to dose received. This population will be used for all data summaries.
- **The Pharmacodynamic Intention To Treat (PD-ITT) Analysis Set.** All patients in the repeat dose and combination cohorts who received at least one dose of AG019 will be included in the PD-ITT analysis set.
- **The Pharmacodynamic Per Protocol (PD-PP) Analysis Set.** All data from patients in the repeat dose and combination cohorts who received at least 75% of the scheduled doses of AG019* and at least one dose of teplizumab in the combination cohorts and had no major protocol deviations affecting the main PD endpoints at the time point of data collection** will be included in the PD-PP analysis set.

* XXXXXXXXXXXXXXXXXXXXXXX

** XXXXXXXXXXXXXXXXXXXXXXX

All patients to be included in the PD-ITT and PD-PP Analysis sets will be determined before data base lock. The Safety Set is considered the primary analysis dataset, and will be used for safety presentations and all other data summaries (except for PD summaries). All summaries will be performed according to dose received. Baseline presentations will be based on the safety set.

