5.8. Return and destruction of study drug

All patients are required to return all empty medication blisters, partially used blisters and unused blisters to the study site upon completion of treatment or in case of withdrawal. If a patient is lost to follow-up during the treatment phase, the site should make every reasonable effort to obtain the used, partially used and unused blisters.

Unused AG019 capsules will be destroyed by a dedicated drug destruction facility. Local destruction by the site is not allowed unless mandated by the site's local procedures. If unused, used and partially used study drug is destroyed on site, this can only be done after IMP accountability has been performed by the Sponsor or its designee.

Materials used for teplizumab infusions, as well as empty teplizumab vials, can be destroyed locally by the sites. All materials and vials are to be treated as hazardous medical waste per the site's Standard Operating Procedures.

Unused teplizumab vials will be destroyed by a dedicated drug destruction facility. Local destruction by the site is not allowed unless mandated by the site's local procedures. If unused, used and partially used study drug is destroyed on site, this can only be done after IMP accountability has been performed by the Sponsor or its designee.

5.9.Method of Assigning Patients to Treatment

In the AG019 cohorts, all patients (single dose and repeat dose) will be treated with AG019. Registration of every patient will be required through the IRT (see Section 4.4).

In the combination cohorts, the first 2 patients will be treated with AG019 + teplizumab. The remaining 10 patients in each combination cohort will be randomized (4:1) to study drug or placebo. Patients randomized to receive study drug will be treated with AG019 + teplizumab, patients randomized to receive placebo will be treated with AG019-placebo and teplizumab-placebo. Randomization will be done through the IRT.

During the screening and treatment phase, every study visit for every patient will need to be registered in the IRT. Details about the functionality and use of the IRT are found in the IRT manual.

5.10.Blinding

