10.3. Definitions of Study Populations for Analysis

10.3.1The Safety (SAF) Analysis Set

The safety population will include all patients who receive at least one dose of study medication. Only patients with clear documentation that no study medication was received may be excluded from analysis. Patients will be analyzed according to the dose received. This population will be used for all data summaries.

10.3.2The Pharmacokinetic (PK) Analysis Set

For each cohort, all patients who received the IMP as scheduled and provided sufficient samples to reliably estimate the PK parameters will be included in the PK analysis set.

More details on the PK parameters, analysis and presentation of study results will be provided in the SAP.

10.3.3The Pharmacodynamic (PD) Analysis Set

For each cohort, all patients who received the IMP as scheduled and provided sufficient samples to reliably estimate the PD parameters will be included in the PD analysis set.

More details on the PD parameters, analysis and presentation of study results will be provided in the SAP.

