6.3.2 Summary Statistics

Descriptive statistical methods will be used to summarize the data from this study. Unless stated otherwise, the term descriptive statistics refers to number of patients (n), mean, median, standard deviation (SD), standard error of the mean (SEM), minimum and maximum for continuous data and counts and percentages for categorical data.

Summary statistics will be presented per cohort (based on age group and number of capsules), treatment group and assessment time and/or visit, as applicable. The groups will be divided into single dose for 2 and 6 capsules, repeat dose for 2 and 6 capsules, Active and Placebo. See Table 1 for details.

Table 1

Cohort	Treatment	Number of AG019 capsules per day	Total Number of teplizumab infusions	Age Group
AG019 Cohort 1	AG019, single dose	2	NA	Adults
AG019 Cohort 1	AG019, repeat dose	2	NA	Adults
AG019 Cohort 2	AG019, single dose	6	NA	Adults
AG019 Cohort 2	AG019, repeat dose	6	NA	Adults
AG019 Cohort 3	AG019, single dose	2	NA	Adolescents
AG019 Cohort 3	AG019, repeat dose	2	NA	Adolescents
AG019 Cohort 4	AG019, single dose	6	NA	Adolescents
AG019 Cohort 4	AG019, repeat dose	6	NA	Adolescents
Combination Cohort 1	AG019, repeat dose + teplizumab infusion	6	12	Adults
Combination Cohort 1	Placebo capsules, repeat dose + Placebo infusion	6	12	Adults
Combination Cohort 2	AG019, repeat dose + teplizumab infusion	6	12	Adolescents
Combination Cohort 2	Placebo capsules, repeat dose + Placebo infusion	6	12	Adolescents

NA: not applicable

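### SAP section 5 defines the safety and PD analysis sets by receipt of active drug, so as written no placebo patient belongs to any of them

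*SAP*

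**What the plan says.** SAP section 5 names the safety set as the primary analysis dataset and defines three sets by what the patient received.

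- **Safety set (SAF):** "The safety population will include all patients who received at least one dose of AG019". The next sentence is "Only patients with clear documentation that no study medication was received may be excluded from analysis".
- **PD-ITT:** "All patients in the repeat dose and combination cohorts who received at least one dose of AG019".
- **PD-PP:** at least 75% of scheduled AG019 doses, "and at least one dose of teplizumab in the combination cohorts", and no major protocol deviation affecting the main PD endpoints. Two footnotes to this definition are redacted.

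None of the three mentions placebo. Protocol 10.3.1 defines the safety set differently: "The safety population will include all patients who receive at least one dose of study medication", followed by "Patients will be analyzed according to the dose received". On what the controls are given, protocol 5.9 says that "patients randomized to receive placebo will be treated with AG019-placebo and teplizumab-placebo". On reporting, SAP 6.3.2 says: "The groups will be divided into single dose for 2 and 6 capsules, repeat dose for 2 and 6 capsules, Active and Placebo". Table 1 of the SAP then has one placebo row for each combination cohort.

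**The concern.** A patient given placebo for both components never receives AG019 or teplizumab. Applied as written, the SAP's rules therefore leave the whole control group out of the primary analysis dataset and out of both PD sets, while the same document plans placebo groups for its summaries. A reader of the study report could not match the stated definitions to the placebo columns.

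There is also a practical point about blinding. SAP section 5 fixes PD set membership before database lock, and SAP 6.9 says decisions on blinded subjects are taken before the blind is broken for the third interim analysis. A rule based on capsules and infusions taken, whether active or placebo, can be applied without knowing the allocation. A rule based on receipt of active drug cannot.

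**Working it through.** **1. The plan's own total.** Four AG019 cohorts of up to 6 repeat-dose patients and two combination cohorts of 12 give 4 × 6 + 2 × 12 = 48. This reproduces the maximum of 48 in SAP 4.2.

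**2. Number of controls.** In each combination cohort the first 2 of 12 patients are open-label active and the other 10 are randomised 4:1 (protocol 5.9, SAP 4.1.2).

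- Placebo per cohort: 10 × 1/5 = 2. Active: 2 + 8 = 10.
- Two cohorts: 4 placebo patients.
- Share of combination patients: 4/24 = 16.7%. Share of randomised patients: 4/20 = 20%. Share of the control group: 4/4.

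**3. Set sizes, literal against intended (no replacements).**

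| Set | Intended | Literal |
|---|---|---|
| SAF, distinct patients: 8 single dose + 16 new repeat dose + 24 combination | 48 | 44 |
| PD-ITT, 6 repeat-dose patients per AG019 cohort | 48 | 44 |
| PD-ITT, 4 repeat-dose patients per AG019 cohort | 40 | 36 |

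On the literal reading, 2 of the 12 rows of Table 1 would be empty.

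**4. PD-PP.** SAP 6.3.6 plans 6 × 56 = 336 capsules for every combination patient. If the 75% rule is counted that way (an assumption, because the footnote on AG019 is redacted), the threshold is 0.75 × 336 = 252. A fully compliant placebo patient scores 336/336 if placebo capsules count and 0/336 if they do not. The teplizumab condition carries no footnote of its own.

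**5. Does study medication include placebo?** Protocol 10.3.1 does not define the term. Protocol 5.7 counts the placebos as study drug and protocol 4.5 counts them as IMP. Protocol 5.9 contrasts study drug with placebo when describing the randomisation. The weight of the text favours inclusion.

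**6. What was probably meant.** The Table 1 placebo rows show 6 in the AG019-capsule column and 12 in the teplizumab-infusion column. SAP 6.3.6 applies the 336-capsule total to all combination patients. The CRF question cited in SAP 6.3.8 refers only to the teplizumab infusion, although placebo patients are infused too. The active name thus often stands for the component. It does not always: SAP 4.1.2 adds placebo in brackets after AG019, and 6.3.6 names the teplizumab placebo explicitly.

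**7. What the shorthand reading does not cover.** If AG019 means any capsule, a combination patient who had an infusion and no capsule still fails the SAP's inclusion sentence but satisfies protocol 10.3.1. The documents give no basis for estimating how often this would happen.

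**The case against.** The strongest reply is that the SAP already settles the matter. The second sentence of the safety-set definition permits exclusion only when no study medication was taken, a placebo group is named, and Table 1 reserves rows for it. Shorthand is common in both documents: adverse event tables refer to an AG019 treatment period, compliance outputs are titled by the active drug, and protocol 7.3.3.2 lists a teplizumab infusion for every combination patient. The need to decide PD membership blind also points to the intended reading, because only a rule on capsules and infusions taken would work. PD-PP rests partly on redacted footnotes that may deal with placebo, and SAP 6.3.2 qualifies its groupings as applicable, so placebo groups in the PD summaries are an inference.

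Most of this stands, and it is why the likely number of excluded patients is 0. It does not make the definitions correct. SAF and PD-ITT carry no footnote, the safety-set definition conflicts with its own second sentence, and the SAP names placebo elsewhere but not where membership is fixed. The gap for a patient with an infusion and no capsule remains even when the shorthand is accepted.

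**Conclusion.** The concern holds, as a minor wording defect. The written definition of the primary analysis dataset does not describe the population that the SAP's tables plan to show, and it is narrower than protocol 10.3.1. The effect ranges from 0 patients excluded (the reading that SAP 6.3.2, Table 1 and 6.3.6 support) to 4 of 24 Phase 2a patients, all of them controls (the literal and unlikely reading). The upper figure assumes full enrolment and an exact 4:1 split in each cohort. Confidence is high for SAF and PD-ITT, and somewhat lower for PD-PP because of the redacted footnotes. The study is descriptive, so no test is affected, and a literal misapplication would be visible at once.

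**What to change.** Reword SAP section 5 as follows.

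- **SAF:** at least one dose of any study medication (AG019, teplizumab or either matching placebo), analysed by dose received, in line with protocol 10.3.1.
- **PD-ITT:** at least one dose of AG019 or matching placebo, in the repeat-dose and combination cohorts.
- **PD-PP:** the same exposure conditions as now, applied to AG019 or matching placebo and to teplizumab or matching placebo, so that membership can be judged blind.

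As a separate and optional documentation point, SAP 6.1 could record that PD-ITT and PD-PP replace the single PD set of protocol 10.3.3.

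The cost is SAP wording only. No data collection, table shell or reporting group changes, and the placebo rows of Table 1 stay as they are.
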